## **PROTOCOL SUMMARY**

Title:	Phase 2 placebo-controlled randomized trial of LACTIN-V ( Lactobacillus crispatus CTV-05) among women at high risk of HIV acquisition in Durban, South Africa
Phase:	2
Population:	Non-pregnant women age 18 – 23. Enrolment will be continued until 60 women are randomized into the study
Number of Sites:	One site in Durban, South Africa: FRESH Clinic: Umlazi, KZN
Study Duration:	Duration: 90 weeks after enrolment of the first participant
Participant Participation:	10 weeks (64 days) per participant
Description of Agent:	Lactobacillus (L.) crispatus CTV-05 (LACTIN-V) contains a naturally occurring vaginal strain of L. crispatus CTV-05, preserved as a powder applied by a vaginal applicator.
	LACTIN-V at 2 x 10  cfu/dose or matching placebo will be administered by vaginal applicator once daily for 5 consecutive days, followed by twice weekly for 3 consecutive additional weeks.
Primary Objectives:	1: Determine the effect of repeat dosing of LACTIN-V (2 x 10  cfu/dose) on genital tract inflammation in young South African women at risk of HIV.
	2: Determine the ability of LACTIN-V to promote a Lactobacillus - dominant vaginal microbiota in young South African women at risk of HIV.
	3: Determine the safety and acceptability of LACTIN-V in a population of young South African women at risk for HIV.
Description of Study Design:	See schematic
Time to Complete Enrolment:	65 weeks
Keywords:	Vaginal microbiome, lactobacilli, HIV risk, vaginal mucosa

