proinflammatory cytokines in vaginal fluid and the lowest numbers of CD4+ HIV-target cells in the endocervix.  Unfortunately, only a small fraction of the population had this microbial phenotype (8/94, 9%). The far more prevalent *L. iners* did not confer the same anti-inflammatory effect, nor protection against HIV infection. In the FRESH cohort, when participants transition from a higher CT (more diverse) to a lower CT (less diverse. more Lactobacillus-dominant) the concentrations of genital cytokines dropped.33 Cervicovaginal lavage (CVL) from women with BV has lower SLPI, higher proinflammatory cytokines, and lower anti-HIV activity compared to CVL of women with Lactobacillus dominant microbiota. In the presence of the proinflammatory stimulus of BV, colonization with H2O2-producing Lactobacillus species, like *L. crispatus*, is associated with lower quantities of vaginal cytokines. Vaginal inoculation of anotobiotic mice with L. crispatus is associated with significantly lower numbers

[figure not shown]

Figure 1: Graphical representation of our hypothesis that *L. crispatus* protects agains HIV acquisition through three complimentary pathways: 1) decreased inflammation in genital mucosa; 2) reduced number of activated CD4+ T-cells in endocervix; and 3) reduction of infectious viral particles in genital secretions.

of activated CD4+ T cells in the genital tract compared to *Prevotella bivia*. *In vitro*, several *L. crispatus* strains demonstrated anti-viral effects on HIV, as well as inhibition of viral replication in tissue. Cervicovaginal secretions from women with *L. crispatus* dominant microbiota demonstrate increased HIV-trapping activity compared to *L. iners*-dominated communities. Acidic vaginal secretions characteristic of a *Lactobacillus*-dominant microbial community both trap and inhibit HIV. We will explore these three potential mechanisms of action (Figure 1) in the proposed LACTIN-V clinical trial.

[figure not shown]

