# 2.3 Preliminary Studies on increased HIV acquisition and mucosal inflammation in young South African women

*Lactobacillus*-deficient cervicovaginal bacterial communities are associated with increased HIV acquisition and mucosal inflammation in young South African women: We recently characterized cervicovaginal microbiota in a prospective cohort study of healthy HIVuninfected South African women monitored with high frequency HIV testing. Sequencing of the bacterial 16S rRNA gene revealed the presence of four distinct cervicovaginal bacterial cervicotypes, or "cervicotypes" (CTs), two of which had low diversity and were dominated by either *L. crispatus* (CT1, 11% of participants) or *Lactobacillus iners* (CT2, 32%), and two high diversity CTs dominated by *Gardnerella vaginalis* (CT3, 28%) or a bacterial genus other than *Lactobacillus* or *Gardnerella* (CT4, 28%) (Fig. 2A).  The most abundant taxa in CT4 were anaerobic genera including *Prevotella*, *Gardnerella*, *Sneathia* and *Megasphaera*. Individuals with CT4 communities were at over 4-fold higher risk of acquiring HIV compared to those with *L. crispatus* dominance (Fig. 2B). They further had elevated genital cytokine levels (Fig. 2C) and 17-fold increased numbers of cervical HIV target cells (Fig. 2D) , providing a plausible biological mechanism for the observed increase in infection. We identified specific bacterial taxa linked with HIV infection, showing that *Prevotella melaninogenica*,

**Figure 2: Cervicovaginal microbiome is associated with genital inflammation and increased HIV acquisition. A)** Bacterial 16s rRNA gene sequencing reveals 4 cervicovaginal community types ("CTs") in women in FRESH. **B)** Kaplan-Meier curve showing HIV infections in each CT group over time. Acquisition curves for CT2 (n=65 individuals), CT3 (n=57) and CT4 (n=54) were compared with the acquisition curve for CT1 (n=23). Log-rank (Mantel-Cox) test-based p values and Mantel-Haenszel hazard ratios (HR) are displayed. **C)** Principal component 1 (PC1) of 28 measured cytokines shows increased soluble markers of genital inflammation in women with more diverse cervicovaginal bacterial communities. **D)** Flow cytometry analysis of HIV target cell numbers in in cytobrushes from 169 individuals, grouped by CT. Data are summarized as median and IQR. Kruskal-Wallis test with Dunn's post hoc analyses (\*p<0.05).

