*Prevotella bivia* and *Sneathia sanguinegens*, among other anaerobes, were significantly more abundant in individuals who subsequently acquired HIV.  This association was significant in women without co-infection with STIs, confirming a clear association between bacteria and both inflammation and HIV acquisition.

Using cytobrush samples from the FRESH cohort we demonstrated that women with a more diverse, non-*Lactobacillus* dominant microbiome (CT4) had significantly higher numbers of HIV target cells. In addition, these women had increased concentrations of Th17 cytokines, suggesting higher numbers of Th17+ T cells.  Women with the highest levels of vaginal proinflammatory cytokines had higher number of activated (CD38+ HLA- DR+) CCR5+CD4+ T cells vs. women with the lowest levels (p = 0.0361) (Fig. 3). Antigen presenting cells from women with CT4 had significant upregulation of multiple proinflammatory cytokine gene

such as *IL1A* (5.8-fold), *IL1B* (4.3-fold), *TNF* (6.5-fold), *IL10* (10.6-fold), *IFNB1* (23.4-fold), *IL23A* (7.3-fold), and *IL6* (8.9-fold) vs. CT1 or CT2.  None of these difference in subset numbers or transcription were seen when comparing immune cells from peripheral blood.

[figure not shown]

Figure 3. Women with less genital inflammation or with *L. crispatus* dominant microbiota have lower numbers of cervical HIV target cells. A. Women in FRESH cohort with the lowest quintile of vaginal cytokines had fewer activated cervical CD4+ T cells than women in the highest quintile of inflammation.

**B.** Women with *L. crispatus*dominant microbiota (CT1) had 17fold lower number of activated CD4+ T cells vs. those with a diverse vaginal microbial community (CT4)

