Safety results: Of the 120 AEs that occurred, 108 (90%) were mild and only 12 (10%) were moderate in severity; no grade 3 or 4 AEs or SAEs occurred, and no deep epithelial disruption was seen during colposcopic evaluation.  Furthermore, AEs were evenly distributed between the LACTIN-V and placebo groups.

Efficiency of colonization: Sixty-one percent of the 18 women randomized to the LACTIN- V group were colonized with *L. crispatus* CTV-05 at Day 10 and/or Day 28. Among LACTIN-V users with complete adherence to the study regimen, 78% were colonized at Day 10 and/or Day 28. 

Effect of endogenous bacteria on vaginal colonization of exogenous *L. crispatus* CTV-05: The median vaginal concentrations of seven BV-associated bacteria declined in all participants between screening, when metronidazole treatment for BV was started, and enrolment. In participants who subsequently colonized with *L. crispatus* CTV-05, this trend was maintained at the Day 28 Visit when levels of six species were below limits of detection, with up to 7-log10 reductions in median values. In contrast, among participants who did not colonize with CTV-05, the concentrations of BV-associated bacterial DNA, especially those known to create a biofilm in the vagina [i.e., *A. vaginae* (p=0.04) and *G. vaginalis* (p=0.19)], resurged between enrolment and Day 28. Overall, this study provides evidence that vaginal colonization with a *L. crispatus* LBP can reduce colonization with diverse microbes, and potentially decrease inflammation and HIV risk.  We will evaluate the effect of LACTIN-V on the vaginal microbiome, expecting a shift to a *L. crispatus* dominant cervicotype.

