LACTIN-V—if determined to be a safe and effective live biotherapeutic product (LBP)—has the potential to offer women a sustained, coitally independent, multi-purpose prevention product that promotes vaginal health and provides protection from HIV and potentially other STIs. By exploring the effects of LACTIN-V on genital tract mucosal immune markers associated with increased HIV susceptibility in young women, the ability of LACTIN-V to colonize the vagina and support a *L. crispatus*-dominant cervicotype in the female genital tract, and the safety of LACTIN-V in young South African women, we aim to provide critical data to aid in the continued development of vaginally administered LACTIN-V to prevent HIV-acquisition in women. The use of a safe LBP is an important paradigm shift in the development of HIV prevention technologies. LACTIN-V serves as an attractive alternative to the use of antiretroviral drug formulations currently under development. In addition, we will use molecular diagnostic technology to detect the effect of *L. crispatus C*TV-05 on the vaginal microbiota during follow-up.

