#### 3.4 Study Outcome Measures

#### 3.4.1 Primary/ Secondary Outcome Measures

# *Primary / Secondary Outcome Measures for Objective 1 (effect on genital tract proinflammatory cytokines and HIV target cells)*

The proportion of participants with decreased genital tract proinflammatory cytokines and HIV target cells at 6 and 10 weeks of follow up, compared to levels at the baseline FRESH Study Visit, and Randomization Visit on Day 8 of the study (after treatment with Metronidazole is completed).

Our outcome will be a change after 4 weeks of treatment with LACTIN-V in comparison to

placebo, for the following:

- i. a decrease of the concentrations of proinflammatory cytokines in genital fluid that have been associated with risk for HIV acquisition,
- ii. a decrease in the number of activated HIV target cells (i.e. CD4+/CCR5+/HLA-DR+/CD38+ T cells) in the endocervix and
- iii. an increase the anti-HIV effect of vaginal secretions relative to placebo.

*Primary / Secondary Efficacy Outcome Measures for Objective 2 (promoting Lactobacillusdominant microbiota)* 

1:

The proportion of participants with increased *Lactobacillus*-dominant vaginal microbiota in young South African women, compared to levels at randomization (Day 8) after completion of metronidazole. Measured will be overall *Lactobacillus* species, as well as *Lactobacillus crispatus*, *Lactobacillus jensenii*, *Lactobacillus gasseri*, and *Lactobacillus iners*.

Our primary outcome is the presence of *Lactobacillus*-dominant vaginal microbial cervicotypes after 4 weeks of treatment with LACTIN-V, and following the post- dosing phase at Day 64.

Secondary outcomes include comparison of *L. crispatus* vs. *L. iners* prevalence between treatment groups, persistence of colonization after stopping therapy, effect of sex and/or vaginal hygiene practices on colonization by lactobacilli, and stability of vaginal microbial communities over time in the treatment vs. placebo group.

2:

The proportion of participants with a positive BV diagnosis in each study arm by Day 64.

BV is defined Nugent score 7-10. Following FDA guidance all BV diagnoses during follow-up visits are considered incident, as they occur at least 22-30 days after the commencement of Metronidazole treatment and consequently are treatment failures or new infections. For the purpose of this trial, treatment failure and new infection will both be considered recurrent BV.

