## 4.0 STUDY DESIGN

This is a Phase 2 randomized double-blind placebo-controlled trial to assess the impact of the live biotherapeutic product LACTIN-V containing *Lactobacillus crispatus* CTV-05 on the vaginal microbiome of young women in South Africa at high risk of HIV acquisition.

The study will also assess the safety of LACTIN-V by comparing the incidence of AEs between women randomized to LACTIN-V or placebo.

We will conduct a randomized, placebo-controlled trial of LACTIN-V in a cohort of young South African women with a non-*Lactobacillus* dominant microbiota, who are sexually experienced, age 18 to 23 years. Enrolment will be continued until 60 women will be randomized into the study.

Eligible women will be treated with oral metronidazole 400 mg twice daily for seven days and will then be randomized 2:1 to LACTIN-V vs. placebo.

Within 8-48 hours of taking the final metronidazole dose, women will receive the study product for five consecutive days, followed by a twice weekly dose for three additional weeks.

After enrolment and metronidazole treatment, women will be followed throughout the 4 weeks of dosing and the 4 weeks of post-dosing phase for a total of 10 weeks (until approximately Day 64).

The primary outcome (**Objective 1**) focuses on the ability of the *L. crispatus* CTV-05 to acutely decrease genital tract inflammation (as a marker of HIV susceptibility). This will be assessed by collecting cervicovaginal fluid and endocervical immune cells at randomization (Day 8), after 4 weeks of treatment with the LACTIN-V vs. placebo (Day 36), and after 4 weeks of post-dosing phase (Day 64).

Direct anti-HIV activity will be assessed with *in vitro* HIV infection assays using vaginal fluid samples from randomization and after treatment: Randomization Visit (Day 8), Follow-up Visit (Day 36), and Final Visit at Day 64.

A secondary outcome (**Objective 2**) is to assess the ability of the *L. crispatus* CTV-05 to establish durable vaginal colonization as with the potential as a self-sustaining prevention strategy. This will be assessed by characterization of the vaginal microbiome at the baseline FRESH Study Visit, and the end of treatment (Day 36) and at the Final Visit (Day 64), after 4 additional weeks during the post-treatment phase.

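### Is the Objective 2 primary outcome wrong because it counts L. iners dominance as well as L. crispatus dominance?

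*Combined protocol and SAP*

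**What the plan says.** Objective 2 reads the same in the Protocol Summary and in 3.3.1: "Determine the ability of LACTIN-V to promote a" vaginal microbiota dominated by Lactobacillus. The hypothesis in 3.1, also given in 2.5, is likewise about a persistent Lactobacillus-dominant community. Under that objective, 3.4.1 names as primary the presence of Lactobacillus- "dominant vaginal microbial cervicotypes after 4 weeks of treatment with LACTIN-V", and again at Day 64; 11.2 repeats it.

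Other places speak of the species or the strain. Section 2.4 announces an evaluation of the "effect of LACTIN-V on the vaginal microbiome, expecting a shift to a" type dominated by L. crispatus. Section 2.5 mentions support for an L. crispatus- "dominant cervicotype in the female genital tract". Section 4.0 describes Objective 2 as testing the ability of L. crispatus "CTV-05 to establish durable vaginal colonization as with the potential as a self-sustaining prevention strategy". Section 2.1 says that L. iners "did not confer the same anti-inflammatory effect, nor protection against HIV infection".

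Species-level outcomes are also listed. Section 3.4.1 has L. crispatus against L. iners by arm as a secondary outcome, CTV-05 colonization as item 3 and cervicotypes I to IV by arm as item 4. Section 11.2 adds L. crispatus quantity and presence of the CTV-05 strain. Section 11.5 includes CTV-05 in the Objective 2 primary analysis and assigns Fisher's exact test to strains and cervicotypes.

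**The concern.** LACTIN-V contains one strain of L. crispatus, and the background argues that lactobacilli are not interchangeable for HIV risk. An outcome that scores L. iners dominance as success seems to miss what the product is meant to do.

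Two harms would follow. If L. iners dominance is about equally common in both arms among women without L. crispatus dominance, it dilutes a true L. crispatus effect. If it is commoner on LACTIN-V, the pooled outcome can differ between arms with no L. crispatus effect at all. The cohort figures make this look serious, since L. iners was the more frequent of the two Lactobacillus-dominated types.

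**Working it through.** **1. Cohort mix.** Section 2.3 gives the group sizes: "Acquisition curves for CT2 (n=65 individuals), CT3 (n=57) and CT4 (n=54) were compared with the acquisition curve for CT1 (n=23").
- L. iners share of Lactobacillus-dominated women: 65/(23+65) = 65/88 = 74%.
- L. iners share of women outside CT1: 65/(65+57+54) = 65/176 = 36.9%.

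These describe the general cohort. The trial enrols only women with Nugent 4-10 (5.1) and gives all of them metronidazole before randomization. The documents give no cervicotype rates after that treatment.

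**2. The plan's own power figure.** Section 11.3 states power above 88% for 10% vs 50%, with 20 placebo and 40 LACTIN-V women and a two-sided Fisher's exact test at 5%. Exact enumeration gives 0.891, so the figure reproduces. It belongs to the Objective 1 cytokine endpoint. No rate, effect or power is stated for Objective 2, so nothing stated there can be wrong.

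**3. What pooling could do.** Let c be the CT1 rate in an arm and s the L. iners-dominant share among its non-CT1 women. Then P(pooled) = c + (1-c)s. All values of c and s below are assumptions. The 10% vs 50% contrast is borrowed from Objective 1, and CT1 alone then has power 0.891.

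| s placebo | s LACTIN-V | pooled rates | pooled power |
|---|---|---|---|
| 5% | 5% | 14.5% vs 52.5% | 0.815 |
| 10% | 10% | 19.0% vs 55.0% | 0.733 |
| 20% | 20% | 28.0% vs 60.0% | 0.572 |
| 36.9% | 36.9% | 43.2% vs 68.5% | 0.410 |
| 60% | 60% | 64.0% vs 80.0% | 0.219 |
| 36.9% | 20% | 43.2% vs 60.0% | 0.171 |
| 10% | 36.9% | 19.0% vs 68.5% | 0.949 |

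With equal s the pooled difference is (1-s)(c1-c0), always smaller than the CT1 difference. With unequal s it is larger once s on LACTIN-V exceeds (1-c0)/(1-c1) = 0.90/0.50 = 1.80 times s on placebo. Neither the direction nor the size of the effect is fixed by anything in the documents.

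**4. Significance without a CT1 effect.** With c = 10% in both arms and s = 10% vs 36.9%, the pooled rates are 19.0% vs 43.2%. The pooled test rejects 41% of the time and the CT1 test 2.8%. This is not a false positive for Objective 2 as written: in that scenario LACTIN-V really does raise the proportion with Lactobacillus dominance.

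**5. Outcome against objective.** The outcome has to answer the listed objective, and both are at genus level. The species statements have a different standing. Section 2.4 states an expectation in the background, and 2.5 is rationale. The colonization aim in 4.0 has its own outcome, item 3 of 3.4.1. Some of the protocol's evidence also fits the genus level: 2.3 contrasts gene expression in CT4 ("8.9-fold) vs. CT1 or CT2"), and 2.1 reports falling cytokines when women moved to a less diverse, more Lactobacillus-dominant type.

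**The case for a change.** The strongest case on the other side is that the protocol tells two stories about Objective 2 and the named primary outcome serves only one. The statement in 2.1 about L. iners is plain, and the product is L. crispatus. The remedy would use the same sequencing data and a Fisher comparison already planned, so it looks cheap.

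Part of this stands. A pooled result cannot be read as an L. crispatus effect without the species tables, and if L. iners shares are similar by arm, pooling costs power for that question. But those tables are planned by arm, so an L. iners-driven result would be visible. CT1 would not stand alone either: it can reflect a woman's own L. crispatus, so CTV-05 detection would still be needed for attribution. And making CT1 primary replaces a listed primary objective with a narrower one, by protocol amendment with ethics approval (14.2). Reasonable statisticians could choose either.

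Two further points are true but separate. Section 4.0 calls Objective 2 secondary, whereas 3.3.1 lists it as primary. Section 11.2 words the outcome for the LACTIN-V arm, whereas 11.5 compares the two groups. These are inconsistencies of wording; 11.5 already specifies the between-arm comparison, and neither bears on pooling. Finally, pooling is itself a reading of the plural in 3.4.1 together with 2.3. It is the natural reading, but no explicit rule is given.

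**Conclusion.** The concern does not hold. The outcome named primary fits Objective 2 and the hypothesis as the protocol lists them, and the species and strain questions are covered by planned outcomes with a planned test. The 74% L. iners share is correct for the source cohort but is not a post-metronidazole rate in the trial population. The power comparison rests entirely on assumed rates: at an assumed CT1 contrast of 10% vs 50%, the scenarios put pooled power between 17% and 95%, against 89% for CT1 alone. That shows sensitivity to unknown rates and does not demonstrate a loss. Preferring CT1 as the primary outcome is a legitimate view of the research question, but keeping the genus-level outcome is not an error.

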## 5.0 STUDY ENROLMENT AND WITHDRAWAL

The study plans to enrol non-pregnant women, age 18 to 23 years, diagnosed with a non-*Lactobacillus* dominant microbiota (diagnosed by Nugent 4 - 10).

Enrolment will be continued until 60 women have been randomised into the study. Eligibility criteria for participation in the study are described in detail in sections 5.1 and 5.2.

The consent process will be completed during the Enrolment Visit 1 (Day 1) to determine eligibility. Pregnant women, men and children are excluded from study participation (see section 14.4).

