#### 5.1 Subject Inclusion Criteria

Participants must meet all of the inclusion criteria in order to be eligible to participate in the study:

- 1. FRESH study participant.
- 2. Capable of reading and writing English or isiZulu and voluntarily provide written informed consent to participate in the study and comply with all study procedures
- 3. HIV-negative
- 4. Nugent score 4-10 on vaginal Gram stain
- 5. Otherwise healthy women, 18–23 years of age on the day of enrolment
- 6. Regular predictable menstrual cycles or amenorrhoeic for at least 3 months due to use of a long-acting progestin.
- 7. Willing to complete 7-day course of oral metronidazole.
- 8. Willing to be asked questions about personal medical health and sexual history
- 9. Willing to apply study agent vaginally and comply with study examinations
- 10. Willing to self-administer Study Product on dosing days that do not coincide with regular FRESH study visits.
- 11. Agree to try to abstain from sexual intercourse 12 hours prior to study visits that include a gynaecological exam (Randomization Visit 3, Follow-up Visit 11, Final Visit 19).
- 12. Agree to try to abstain from sexual intercourse for 12 hours after study product administration to ensure that the product will remain inside the vagina.
- 13. Agree to abstain from the use of any other vaginal product throughout the trial period from the time of enrolment through the end of the study. Note: Intravaginal products include contraceptive creams such as Gynol II, gels, foams, sponges, lubricants not approved by the study investigators, tampons and douches.
- 14. Must be stable on a reliable method of long-acting birth control and agree to remain on, for the duration of the study (if of childbearing potential) or, of non-childbearing potential (permanently sterile).

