#### 5.3 Treatment Assignment Procedures

#### 5.3.1 Randomization Procedures

Women will be randomized at the Randomization Visit 3 (Day 8) upon completion of the initial standardized antibiotic treatment with 2 x 400 mg daily over 7 days of oral metronidazole.

Women will be randomly assigned to receive LACTIN-V at  $2 \times 10^9$  cfu/dose or placebo in a 2:1 ratio. Enrolment will be continued until 60 women are randomized.

The list of randomized treatment assignments will be prepared by a statistician not involved with the study, and provided to the pharmacy, who will label the applicator pouches and cartons. Each carton will contain 11 study treatment applicators and be sequentially numbered according to the randomization scheme in a 2:1 (LACTIN-V to placebo) ratio.

Disenrolled participants before randomization will be replaced until 60 women are randomized into the study. Once randomized, participants will not be disenrolled.

Participants who test HIV-positive after randomization, will discontinue study product, but continue follow-up and attend all remaining study visits to monitor for adverse events. HIV-specific care, including the provision of antiretroviral treatment and ongoing management will be provided by the FRESH Study.

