# 7.9 Unscheduled Visit

An unscheduled visit following a participant's request or the site investigator's recommendation should be recorded on the appropriate CRF. The following procedures and assessments may be performed at the unscheduled visit:

- 1. Staff will review symptoms, concomitant medications and any medical problems since the last visit, which will be recorded on the appropriate CRF. Additionally, the participant will be asked to provide exact dates and times of the study product administration.
- 2. Medical, gynaecological and sexual history to include assessment of STI risk
- 3. Symptom-directed physical and pelvic examination by a study physician or nurse that will include vital signs, including temperature, and examination of respiratory and cardiovascular systems, as well as assessment of symptoms and adverse events
- 4. The pelvic examination will be conducted in the following order:
  - a. Examination of the external genitalia
  - *b.* Speculum insertion and examination of vagina, fornices and cervix with naked eye. Water will be used to ease speculum insertion. No lubricant should be used as it could contain chlorhexidine which may kill *Lactobacillus.*
  - c. Vaginal pH
  - d. Vaginal swab for Gram stain (Nugent scoring system)
  - e. Two Vaginal swabs for complete mucosal sampling including identification of vaginal bacteria, lactobacilli species, cytokines and HIV target cells as well as multiomic (e.g. proteomics, metabolomics, etc.) testing
  - f. Vaginal swab for prostate specific antigen testing as a proxy for recent exposure to semen
  - g. Vaginal swab for STI testing if indicated by symptoms
  - h. Cervical (or vaginal) swabs for nucleic acid amplification of N. gonorrhoeae, and C. trachomatis.
  - i. A cervico-vaginal lavage sample
  - j. Vaginal swabs for *L. crispatus* identification with qPCR

- 5. Dipstick on clean catch urine; if abnormal, urinalysis (UA) will be performed.
- 6. Rapid Urine βhCG pregnancy test
- 7. All clinical and laboratory findings at the time of the evaluation will be recorded on the CRF. These findings will include observations present on the pelvic exam such as genital findings including location; presence or absence, and character of vaginal or cervical discharge or lesions; and results of any on site tests.
- 8. An additional unscheduled visit as deemed necessary by the site investigator to ensure short-term surveillance will be planned.

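### Every follow-up BV diagnosis is labelled recurrent although women may enter at Nugent 4-6, and no Objective 2 comparison uses entry Nugent

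*Combined protocol and SAP*

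**What the plan says.** Inclusion criterion 4 (section 5.1) is "Nugent score 4-10 on vaginal Gram stain". Section 5.0 describes the entry condition as a non-Lactobacillus "dominant microbiota (diagnosed by Nugent 4 - 10"; it does not require BV.

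The second outcome under Objective 2 in section 3.4.1 is "The proportion of participants with a positive BV diagnosis in each study arm by Day 64". The same text sets the threshold: "BV is defined Nugent score 7-10". It treats all follow-up diagnoses as incident, "as they occur at least 22-30 days after the commencement of Metronidazole treatment and consequently are treatment failures or new infections", and closes with the labelling rule: "For the purpose of this trial, treatment failure and new infection will both be considered recurrent BV".

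Section 5.3.1 describes cartons "sequentially numbered according to the randomization scheme in a 2:1 (LACTIN-V to placebo) ratio" and states no stratification factor. Section 11.2 does not list the BV outcome. Section 11.5 gives Fisher's exact test for lactobacillus strains and cervicotypes, names no analysis for BV, and mentions covariate adjustment only for adverse events.

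**The concern.** Entry and outcome use different Nugent thresholds, and the word recurrent ignores the gap between them. For a woman who qualifies at Nugent 5, there was no BV at the qualifying visit that could fail treatment or come back. If she scores 7 at Day 36 she is nevertheless reported as recurrent BV.

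Two things are at stake. The first is meaning. The background cites relapse in 20-75% of women within 1-3 months of BV treatment (section 2.2), and recurrence of 30% against 45% in the Phase 2b trial (section 2.4). Both concern women treated for BV. A proportion that mixes in women who entered at 4-6 is not the same quantity, and the plan neither gives nor asks for the split.

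The second is precision. Entry Nugent is a plausible predictor of both later BV and Lactobacillus dominance. It is recorded for everyone before randomisation, and with 20 and 40 women per arm a chance imbalance is likely enough to be worth removing.

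**Working it through.** **The plan's own figure.** Section 11.3 states more than 88% power for 10% vs 50%, with 20 and 40 women and a two-sided Fisher's exact test at 5%. Exact enumeration gives 0.891, so it reproduces. It concerns the cytokine endpoint only; no power is stated for BV.

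**Inputs not in the documents.** The share f entering at Nugent 4-6 is not given, nor is any BV rate by entry Nugent. I assume f = 10-50%, a control-type BV risk of 15-30% in the 4-6 group, and 45% in the 7-10 group. The last figure is borrowed from the Phase 2b placebo arm.

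**Share of events mislabelled as recurrent** = f·r₄₋₆ / [f·r₄₋₆ + (1−f)·r₇₋₁₀].
- f = 0.10, r₄₋₆ = 0.15: 0.015 / (0.015 + 0.405) = 3.6%.
- f = 0.30, r₄₋₆ = 0.25: 0.075 / (0.075 + 0.315) = 19%.
- f = 0.50, r₄₋₆ = 0.30: 0.150 / (0.150 + 0.225) = 40%.

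**Validity of the pooled comparison.** With the same mixture in both arms (r₄₋₆ = 0.15, f = 20%, 30%, 50%), unadjusted Fisher's exact test at 20 vs 40 rejects in 3.5-3.7% of trials. Pooling does not inflate type I error.

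**Chance imbalance.** SD of the between-arm difference in f = √[f(1−f)(1/20 + 1/40)].

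| f | SD | P(difference ≥ 15 points), exact binomial |
|---|---|---|
| 0.2 | 0.110 | 0.208 |
| 0.3 | 0.125 | 0.274 |
| 0.4 | 0.134 | 0.307 |
| 0.5 | 0.137 | 0.317 |

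Conditional on the total number entering at 4-6, the same probability is 0.30-0.41. If BV risk differs by 25 points between entry groups (assumed), a 15-point imbalance moves the BV contrast by 0.15 × 0.25 = 0.0375, about 4 points. At 45% vs 30% the standard error of that contrast is √(0.45·0.55/20 + 0.30·0.70/40) = √(0.012375 + 0.00525) = 0.133. The shift is therefore 0.0375/0.133 = 0.28 standard errors.

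**What stratifying buys.** Exact Fisher power for BV at 45% vs 30% is only 18%. At a risk ratio of 0.66 it is 19% if all women enter at 7-10, and 16%, 14% and 11% if 20%, 30% and 50% enter at 4-6 with 15% risk. In simulations at 20 vs 40 under assumed rates, an exact test stratified by entry Nugent held type I error at 3.2-3.8%. It added 0-6 points of power for Lactobacillus dominance and left power for BV within about 0.6 points of the unstratified test. The gain depends on how strongly entry Nugent predicts the outcome.

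**Timing.** The Day 36 window opens at Day 33, which is 33 − 1 = 32 days after metronidazole starts on Day 1. Both scheduled post-dosing stains therefore satisfy the 22-30 day premise. Section 7.9 also lists "Vaginal swab for Gram stain (Nugent scoring system") among procedures that may be done at unscheduled visits, and section 7.8 includes it at discontinuation or early termination. Neither has a minimum day. The outcome runs up to Day 64, and no rule says which stains count.

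**The case against.** The strongest reply is that the endpoint is not a recurrence proportion. What is measured is BV-positive by arm, for all women, and the label is a stated convention that expressly includes new infections. Changing the label alters no count in the between-arm comparison. Admitting Nugent 4-10 is also deliberate: the target is non-Lactobacillus-dominant microbiota, and section 2.1 reports the HIV-risk association whether or not BV criteria are met. All of this stands. It limits the point to labelling, interpretation and precision, and does not remove it.

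A reader might go further and infer three things the documents do not support.
- *That some women counted as recurrences never had BV.* The documents show one qualifying Nugent score per woman; her earlier history is unknown.
- *That pooling biases the treatment comparison.* Randomisation keeps it unbiased in expectation, type I error is controlled, and chance imbalance is ordinary sampling error. The limit on the BV comparison is the sample of 60, not the pooling.
- *That the plan prescribes an unadjusted BV analysis, or that randomisation is known to be unstratified.* No BV analysis is named at all, and the randomisation scheme is not described beyond its ratio. Only the cervicotype comparison is explicitly an unadjusted Fisher test.

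It is also fair to say that the protocol sets up no formal comparison with the Phase 2b rates, and that the timing premise holds for every scheduled post-dosing stain.

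**Conclusion.** The point holds in a limited form. A woman entering at Nugent 4-6 is counted as a recurrence of a condition she did not have, by the trial's own definition, at the qualifying visit. The resulting figure cannot be set beside the cited recurrence rates. Under the assumed inputs, 4-40% of control-type events carry the wrong label; the width of that range reflects the missing split and rates, not a finding about this cohort.

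The between-arm contrast is not biased. An unlucky 15-point imbalance would move it by about 4 points, roughly a quarter of a standard error, if the assumed 25-point risk gap is right. Stratifying by a score already in hand costs no type I error and may add up to about 6 points of power for Lactobacillus dominance. For BV it changes almost nothing. Off-schedule Gram stains need only a counting rule.

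**What to change.** In section 3.4.1, rename the outcome BV (Nugent 7-10) at Day 36 or Day 64. Reserve recurrent for women with Nugent 7-10 at the FRESH Week 5 visit, and report that subgroup's proportion with its own denominator. List BV found at unscheduled, discontinuation or early-termination visits separately, and state how a woman with no scheduled post-dosing stain is counted.

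In section 11.5, name an analysis for BV. Compare both the BV and the Lactobacillus-dominant cervicotype proportions between arms with an exact test stratified by entry Nugent (4-6 vs 7-10), and show both strata.

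This is endpoint and analysis wording only. Entry Nugent is already an eligibility item, so no visit, sample, treatment or sample size changes. The costs are a smaller denominator for the recurrence figure and small strata among the 20 placebo women (4-10 in the 4-6 stratum if 20-50% enter there), so the stratum results should be read descriptively.
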